1. TITLE PAGE

Study Title:	A Multi-Center, Randomized, Double Masked, Placebo Controlled Clinical Study to Assess the Safety and Efficacy of BRM421 Ophthalmic Solution in Subjects With Dry Eye Using a Controlled Adverse Environment (CAE [®]) Model
Investigational Product:	BRM421 Ophthalmic Solution
Indication Studied:	Dry Eye Syndrome (DES)
Brief Description:	This is a multi-center, double-masked, randomized, vehicle-controlled, phase 2/3 CAE study in approximately 200 subjects. (100 per treatment arm).
Name of the Sponsor:	BRIM Biotechnology, Inc. [name]
Protocol Identification:	BRM421-18-C001-PR
Development Phase:	2/3
Study Initiated:	January 15, 2020
Study Completed:	June 23, 2020
NCT number:	NCT04343287
Document Date	IRB approval on December 10 2019
Date of Report:	December 30 2020
Statement of Compliance with Good Clinical Practice	
This study was performed in compliance with the ethical principles of the Declaration of Helsinki and the International Conference on Harmonisation (ICH) Harmonised Tripartite Guideline for Good Clinical Practice (GCP).	
Confidentiality Statement	

3. STUDY PROTOCOL

This was a multi-center, double-masked (participants and research team), randomized, placebo-controlled, phase 2/3 study conducted between January 2020 and June 2020 at 4 sites in the United States (Total Eye Care, Andover Eye Associates, Eye Research Foundation and Midwest Cornea Associates, LLC). This study (ClinicalTrials.gov identifier: NCT04343287) was performed in compliance with the ethical principles of the Declaration of Helsinki and the International Conference on Harmonisation (ICH) Harmonised Tripartite Guideline for good clinical practice (GCP). Institutional Review Board (IRB)/Ethics Committee approval was obtained. All potential subjects provided written informed consent before screening.

After the screening visit, eligible subjects entered a one-week run-in period to receive preservative-free placebo solution bilaterally three times daily (TID) to minimize the placebo effect. Subjects that exhibited improvements in symptoms of dry eye syndrome (DES) at the end of the run-in period, relative to screening values, were disqualified. Eligible subjects were subsequently randomized in a 1:1 ratio to receive placebo or BRM421 Ophthalmic Solution three times daily (TID) in each eye for total 2 weeks, and the efficacy and safety assessments were performed at 1 and 2 weeks after treatment.

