4. STATISTICAL ANALYSIS PLAN

The primary efficacy analyses, including FCS and ODS dryness, were performed using the last observation carried forward (LOCF) imputation method of the intent-to-treat (ITT) population at week 2 for missing values. The treatment effect in each group was calculated by change from baseline in pre-controlled adverse environment (CAE) mode.

The difference from baseline in pre-CAE values for active treatment was tested versus placebo using a two-way ANCOVA model adjusting for baseline at $\alpha = 0.05$. A Wilcoxon rank sum test and a two-sample *t*-test were also assessed where appropriate.

The continuous and ordinal secondary efficacy variables were analyzed with an ANCOVA model adjusting for baseline and also evaluated with a two-sample *t*-test comparing active treatment to placebo. No imputation was performed for secondary efficacy variables.

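### Does calling each arm's change from baseline its treatment effect mislead, given that the run-in removed subjects who improved?

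*Combined protocol and SAP*

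**What the plan says.** Section 3 describes the sequence. Screening came first, and then "eligible subjects entered a one-week run-in period to receive preservative-free placebo solution bilaterally three times daily (TID) to minimize the placebo effect". At the end of that week a selection rule applied: "Subjects that exhibited improvements in symptoms of dry eye syndrome (DES) at the end of the run-in period, relative to screening values, were disqualified". Only afterwards came allocation: "Eligible subjects were subsequently randomized in a 1:1 ratio to receive placebo or BRM421 Ophthalmic Solution". The rule does not say which symptom was scored or how much improvement disqualified a subject.

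Section 4 names FCS and ODS dryness among the primary efficacy analyses, assessed at week 2. It attaches the term treatment effect to a quantity that exists in each arm: "The treatment effect in each group was calculated by change from baseline in pre-controlled adverse environment (CAE) mode". The test, with a significance level of 0.05, follows in the next paragraph: "The difference from baseline in pre-CAE values for active treatment was tested versus placebo using a two-way ANCOVA model adjusting for baseline". A rank sum test and a two-sample t-test are added where appropriate, and the secondary variables are also compared between arms. No within-arm test is mentioned. Neither section says whether baseline is the screening visit or the end of run-in.

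**The concern.** If a subject stays in only when the end-of-run-in score is no better than the screening score, the subjects kept tend to have positive error in the later score and negative error in the earlier one. At week 2 the error is drawn afresh and scores drift back. Measured from the end of run-in, both arms appear to improve. Measured from screening, both may appear to worsen. A reader told that the BRM421 arm's own change is its treatment effect could credit the drug with movement that the selection rule produced.

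ODS dryness is a primary endpoint and a dry-eye symptom, so it is the endpoint most likely to be exposed. The unnamed baseline visit adds to the worry, because the sign of the artefact depends on it.

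**Working it through.** **Inputs from the documents.** About 200 subjects, 100 per arm (title page; 2 x 100 = 200 agrees). One-week placebo run-in, improvers removed, then 1:1 randomisation (section 3). ANCOVA adjusting for baseline, active versus placebo, alpha 0.05 (section 4; two-sided assumed). The documents give no effect size, SD or power, so there is no further design figure to reproduce.

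**Assumptions.** Screening score X1, end-of-run-in score X2, week-2 score Y. Each has SD 1, higher is worse, and the drug has no effect. The rule acts on the score analysed and keeps X2 >= X1. The correlation rho is not in the documents and is varied.

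**Step 1: within-arm change, equal correlations.**
- D = X2 - X1 has variance 2(1 - rho), so E[D | D >= 0] = 2 sqrt((1 - rho)/pi).
- Cov(Y - X2, D) = -(1 - rho), so the slope of Y - X2 on D is -1/2.
- Hence E[Y - X2 | kept] = -sqrt((1 - rho)/pi).
- For rho = 0.3, 0.5, 0.7, 0.8 this gives -0.472, -0.399, -0.309, -0.252 SD. Simulation gave -0.474, -0.397, -0.308, -0.254.
- From screening the slope is +1/2, so the sizes are the same with the opposite sign.

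**Step 2: other assumptions, change from end of run-in.**

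| Assumption | rho 0.3 | 0.5 | 0.7 | 0.8 |
|---|---|---|---|---|
| 0-5 score, SD about 1 point | -0.348 | -0.281 | -0.206 | -0.159 |
| Only improvement above 0.5 SD disqualifies | -0.327 | -0.254 | -0.171 | -0.118 |
| AR(1) correlation | -0.328 | -0.200 | -0.095 | -0.050 |
| AR(1) and the 0.5 SD threshold together | -0.225 | -0.129 | -0.051 | -0.024 |
| Entry only if screening is at or above the mean | -0.793 | -0.598 | -0.412 | -0.319 |

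In the last case the change from screening is -0.145, 0.001, 0.094 and 0.115 SD. An endpoint outside the rule, such as FCS might be, shifts by only 0.05 to 0.12 SD if its errors correlate 0.3 with the symptom's (rho 0.5 to 0.9, or a run-in shift of 0.3 SD at rho 0.7).

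**Step 3: the quantity that section 4 tests.** Selection precedes allocation, so the expected shift is the same in both arms. At rho 0.7 the difference is -0.309 - (-0.309) = 0. Simulated null trials with 100 per arm (1,500 per scenario; rho 0.5, 0.7 and 0.9, plus a persistent run-in improvement of 0.3 SD at rho 0.7) gave:
- adjusted between-arm difference from -0.005 to +0.005 SD;
- ANCOVA type I error 0.049 to 0.055 with end of run-in as baseline, and 0.048 to 0.053 with screening as baseline.

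The simulation standard error is sqrt(0.05 x 0.95/1500) = 0.006, so all of these agree with 0.05.

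**Step 4: would adding the screening score as a second covariate help?** It does not remove the within-arm shift. It cuts residual variance by 2.6% to 8.7% with equal correlations, by 0.7% to 2.1% if the screening to week-2 correlation is 0.1 lower, and by nothing under AR(1). A 9% cut moves 80% power to Phi((1.960 + 0.842)/sqrt(0.91) - 1.960) = Phi(0.977), about 84%.

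**The case for a change.** The strongest case for a change is that both premises are in the text and the repair would be cheap. Section 4 does attach the term to each arm's own change, selection does act on the difference between the two candidate baselines, and under most of the assumptions above the shift is not trivial. Rewording one phrase and naming a visit would cost almost nothing.

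The arithmetic stands, and so does the observation that the wording is loose. The consequence does not.
- The phrase covers the placebo arm as well, so it cannot sensibly mean the causal effect of BRM421. Read with the sentence that follows it, it describes the outcome variable.
- The documents contain no within-arm test and no statement crediting the drug with a within-arm change.
- The feared exaggeration needs the end of run-in to be baseline. From screening, the same selection gives an apparent worsening or, with an entry threshold, something near zero.
- A table note saying that selection produces a change in both arms would claim too much: the rule's symptom and threshold are not given, and FCS is not shown to be part of it.
- The screening covariate is a separate matter of precision. It assumes that dryness was scored at screening, and the title page dates completion to June 2020 and the report to December 2020, so it could only be a supportive analysis after the fact.

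**Conclusion.** The concern is right about regression to the mean but does not reach the analysis. Followed as written, the plan tests the randomised, baseline-adjusted contrast, which is unbiased under the null whichever visit is taken as baseline. Calling a per-arm change a treatment effect is a slip of terminology. The unnamed visit is a missing detail that an analyst would ordinarily fill with the last assessment before randomised treatment, and the validity of the comparison does not depend on that choice.

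The expected within-arm artefact runs from about -0.47 to -0.02 SD from the end of run-in without an entry threshold, and reaches -0.79 SD with one at the mean. All of these figures rest on assumed correlations and on the rule having acted on the analysed score. Within-arm changes should be read as descriptive for that reason. That is a caution for interpretation, and no change to the plan follows.

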4. STATISTICAL ANALYSIS PLAN

The primary efficacy analyses, including FCS and ODS dryness, were performed using the last observation carried forward (LOCF) imputation method of the intent-to-treat (ITT) population at week 2 for missing values. The treatment effect in each group was calculated by change from baseline in pre-controlled adverse environment (CAE) mode.

The difference from baseline in pre-CAE values for active treatment was tested versus placebo using a two-way ANCOVA model adjusting for baseline at $\alpha = 0.05$. A Wilcoxon rank sum test and a two-sample *t*-test were also assessed where appropriate.

The continuous and ordinal secondary efficacy variables were analyzed with an ANCOVA model adjusting for baseline and also evaluated with a two-sample *t*-test comparing active treatment to placebo. No imputation was performed for secondary efficacy variables.

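### Should the ODS dryness ANCOVA also adjust for the second symptom score implied by the run-in rule?

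*Combined protocol and SAP*

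**What the plan says.** Section 4 (Statistical Analysis Plan) names FCS and ODS dryness at week 2 among the primary efficacy analyses, as change from baseline in pre-CAE values, in the ITT population with LOCF. The model is given in one sentence: "The difference from baseline in pre-CAE values for active treatment was tested versus placebo using a two-way ANCOVA model adjusting for baseline". The plan adds, where appropriate, "A Wilcoxon rank sum test and a two-sample" t-test. For the remaining endpoints, "The continuous and ordinal secondary efficacy variables were analyzed with an ANCOVA model adjusting for baseline".

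Section 4 does not say which visit supplies baseline, and it does not name the further term that the label two-way implies.

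Section 3 (Study Protocol) describes a one-week placebo run-in before randomisation, with this rule: "Subjects that exhibited improvements in symptoms of dry eye syndrome (DES) at the end of the run-in period, relative to screening values, were disqualified". It does not name the symptom scale used, and it does not say whether those scores were pre-CAE.

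The title page gives about 200 subjects, 100 per arm, with the study completed in June 2020 and the report dated December 2020.

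**The concern.** Applying the run-in rule requires a symptom assessment at both screening and end of run-in. If that assessment included ODS dryness, each randomised subject has two pre-randomisation values of a primary endpoint. An ANCOVA with one baseline then discards one of them. Both values precede randomisation, so adding the second as a covariate cannot bias the comparison, and it may narrow the confidence interval at almost no cost.

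There is also a question of definition. Adjusting for the screening score and adjusting for the end-of-run-in score give different treatment estimates. With the visit unnamed, a reader might fear that the result depends on an unrecorded choice. FCS is not directly involved, because nothing shows that it was compared across the run-in.

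**Working it through.** **Inputs from the documents.** About 200 subjects, 100 per arm, randomised 1:1; alpha 0.05 (two-sided assumed, since sidedness is not stated); one baseline covariate. The sample size cannot be reproduced, because no effect size, SD, power or dropout is given. No correlations, scale or improvement threshold are given either, so everything below that depends on them is assumed.

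**1. Cost.** With treatment and one covariate, residual df are 200 - 3 = 197; with two covariates, 196. The variance penalty is 197/196 = 1.005, about 0.5%, or one subject in 200.

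**2. Formula for the gain.** Let Y be week 2, B end of run-in and S screening. Adding S to a model with B cuts residual variance by the squared partial correlation:

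(r_YS - r_YB × r_BS)² / [(1 - r_YB²)(1 - r_BS²)]

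- Equal correlation rho: this reduces to (rho/(1+rho))². For rho = 0.4, 0.6, 0.8 it is 8.2%, 14.1%, 19.8%.
- Autoregressive decay: r_YS = r_YB × r_BS, so the gain is 0.

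**3. Effect of the run-in rule.** If any improvement on this same score disqualifies, only B ≥ S remains (higher score taken as worse). Selection raises r_BS and makes the second score more redundant. Example at rho = 0.8: after selection r_BS = 0.922 and r_YB = r_YS = 0.827, so the cut is (0.827 × 0.078)² / [(1 - 0.684)(1 - 0.850)] = 0.00416/0.0474 = 8.8%, against 19.8% without selection.

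Simulated cuts in residual variance (%), 3 million triples per scenario, weekly correlation 0.4 / 0.6 / 0.8. In the mixed structure, 60% of the weekly correlation is stable and the rest decays by a factor of 0.7 per week:

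| Structure | Baseline = end of run-in, selected | Same, unselected | Baseline = screening, selected | Same, unselected |
|---|---|---|---|---|
| Equal | 3.8 / 6.3 / 8.7 | 8.2 / 14.1 / 19.8 | 3.9 / 6.4 / 8.7 | 8.2 / 14.1 / 19.7 |
| Mixed | 1.9 / 2.4 / 1.2 | 4.3 / 5.6 / 3.0 | 3.1 / 5.3 / 7.6 | 6.7 / 11.8 / 17.7 |
| Autoregressive | 0 / 0 / 0 | 0 / 0 / 0 | 1.0 / 3.8 / 8.8 | 2.1 / 8.7 / 20.0 |

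**4. The upper end depends on which score drove the rule.** Suppose disqualification rested on a measure whose run-in change correlates c with the ODS dryness change. Under equal correlation the cut is then 5.7 / 9.6 / 13.1% at c = 0.8 and 7.3 / 12.5 / 17.3% at c = 0.5. If only improvements above 1 SD disqualify, it reaches about 17%. So 9% is not a bound that the documents support; the fair range is 0 to about 20%.

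**5. In power.** At 100 per arm and 80% power, the detectable difference is (1.960 + 0.842) × √(2/100) = 0.396 residual SD. A 9% cut lowers the SE by 1 - √0.91 = 4.6%, equals 100/0.91 = 110 per arm, and raises power to 83.6%. A 19.8% cut equals 100/0.802 = 124.7 per arm and raises power to 87.9%. With selection on the same score, simulated power changed by -0.4 to +3.4 points (baseline at end of run-in) or +0.1 to +3.6 points (baseline at screening).

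**6. Validity.** Both scores precede randomisation, so the planned comparison is sound without the second one. In null trials of 200, type I error was 0.048 to 0.053 for the two-covariate model, 0.049 to 0.052 for the t-test and 0.048 to 0.052 for the Wilcoxon test.

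**The case for a change.** The strongest case for a change is not precision. With both scores in the model, subtracting either from the outcome leaves the treatment coefficient unchanged, so the ANCOVA no longer depends on which visit is called baseline. With one covariate it does depend on it. Switching the visit changed the verdict in 1.0 to 5.2% of simulated null trials, and in 2.4 to 13.2% of trials with an effect set for about 80% power. For the t-test on change, the latter figure is 13.6 to 18.6%; for the Wilcoxon test, 14.2 to 19.9%. ODS dryness is a primary endpoint, and the remedy is one covariate and one sentence.

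The algebra stands, and naming the visit would be good practice. The rest does not amount to a reason to alter the plan:

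- The switching figures describe an analyst who moves between visits. Nothing in the documents suggests that. A placebo run-in intended to reduce placebo response makes the last value before randomisation the natural baseline.
- With that baseline, the extra score is worth least, and under autoregressive decay it is a small net loss.
- The second covariate does nothing for the t-test and Wilcoxon test, so it would not replace a definition of baseline.
- The condition on which the proposal depends, pre-CAE ODS dryness scored at both visits, is not shown. If baseline is the average of the two visits, neither score is unused.

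**Conclusion.** The concern does not call for a change. A single-baseline ANCOVA is standard and valid here; a second pre-randomisation score is an optional gain in efficiency. Its size rests wholly on assumed correlations: about 0 to 9% of residual variance if the run-in rule acted on ODS dryness itself with weekly correlations of 0.4 to 0.8, and up to about 20% if the rule acted weakly or on other symptoms, less about 0.5% for the degree of freedom.

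Each possible remedy falls short. A post hoc two-covariate analysis of a completed trial would leave the primary result standing. The baseline visit is a missing detail, and an analyst would sensibly take it as end of run-in. Pre-specifying a second covariate in a later trial does not alter this plan, and the documents give no correlations from which to show that it would help.

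### Does leaving site unstated in the ANCOVA models of this four-site trial call for a change to the analysis?

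*Combined protocol and SAP*

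**What the plan says.** Section 3 (Study Protocol) describes a "phase 2/3 study conducted between January 2020 and June 2020 at 4 sites in the United States". On allocation it says "Eligible subjects were subsequently randomized in a 1:1 ratio to receive placebo or BRM421 Ophthalmic Solution", with no stratification factor given. The title page describes a "phase 2/3 CAE study in approximately 200 subjects", 100 per arm.

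Section 4 (Statistical Analysis Plan) states that the difference from baseline in pre-CAE values "was tested versus placebo using a two-way ANCOVA model adjusting for baseline", at alpha 0.05. The primary endpoints are FCS and ODS dryness. The supplementary methods for them are given as "A Wilcoxon rank sum test and a two-sample" *t*-test, used where appropriate. For the rest, "The continuous and ordinal secondary efficacy variables were analyzed with an ANCOVA model adjusting for baseline", with a two-sample *t*-test alongside.

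Site is not mentioned anywhere in section 4.

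**The concern.** In a multi-centre trial one expects to read how centre is handled. Here baseline is the only covariate named, and the Wilcoxon and *t*-tests as described adjust for nothing, so the ANCOVA is the only listed method that could carry a site term.

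If sites differ in mean change for reasons that baseline does not explain, and site is left out, that variation stays in the residual and widens the interval for the treatment difference. If randomisation was also balanced within site, the reported standard error is too large for the design and the test rejects less often than 5% under the null. A four-level factor costs only three degrees of freedom, so leaving it out could look like an avoidable loss of power.

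**Working it through.** **What the text establishes.** The primary model is called two-way. In ordinary usage that means two classification factors. Treatment is one; baseline is a covariate and would not normally count. The second factor is unnamed, and in a four-site trial site is an obvious candidate. The phrase could equally be loose wording for treatment plus baseline. So for the primary endpoints the text shows an unnamed term, not an excluded one. The secondary model is not called two-way, so omission is more plausible there, but that sentence need not list every term.

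**Inputs from the documents.** 200 subjects, 100 per arm, 4 sites, alpha 0.05 (taken as two-sided). The documents give no power, effect size, SD, site sizes or between-site variance, so the planned sample size cannot be reproduced beyond 200 / 2 = 100 per arm.

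**Assumptions.** Let r be the site share of residual variance after baseline adjustment, 0 to 10%. The residual SD is set to 1. The effect is the one that gives 80% power by the normal approximation: d = (1.960 + 0.842) × √(2/100) = 0.396 SD.

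**Cost in degrees of freedom.** Without site: 200 − 3 = 197. With site: 197 − 3 = 194. The critical *t* moves from 1.9721 to 1.9723, which is negligible.

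**Interval width, with site relative to without.**
- Allocation balanced within site: ratio = √(1 − r) × 1.9723/1.9721.
- Allocation not balanced: chance imbalance between sites inflates the variance by about 197/194 = 1.0155, so ratio = √[(1 − r) × 1.0155] × 1.9723/1.9721.

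At r = 0 without balance, √1.0155 = 1.0077, so the interval is about 0.8% wider. Break-even without balance solves (1 − r) × 197/194 = 1, giving r = 3/197 = 1.5%. With balance it is about 0.02%.

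**Power.** Noncentral *t* with noncentrality d / √(0.02 × V), where V is the residual variance multiplier. Without site and without balance, V = 1 and power is 79.6% throughout. Without site but with balance, the estimate has variance multiplier 1 − r while its reported standard error still reflects 1. The effective critical value is then 1.9721/√(1 − r), and this gives the proper comparator for the balanced case.

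| r | CI width, balanced | CI width, not balanced | Power without → with site, balanced | Power without → with site, not balanced |
|---|---|---|---|---|
| 0% | +0.01% | +0.8% | 79.6 → 79.6 | 79.6 → 79.0 |
| 2% | −1.0% | −0.2% | 79.9 → 80.4 | 79.6 → 79.8 |
| 5% | −2.5% | −1.8% | 80.2 → 81.6 | 79.6 → 81.0 |
| 10% | −5.1% | −4.4% | 80.9 → 83.6 | 79.6 → 83.1 |

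Power gains are therefore about 1.4 points at 5%, and 2.8 (balanced) to 3.4 (not balanced) at 10%. In equivalent subjects, 200/[(1 − r) × 1.0155] to 200/(1 − r) gives 207 to 211 at 5% and 219 to 222 at 10%.

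**Type I error without site.** If balanced within site, it is P(|T| > 1.9721/√(1 − r)) on 197 df: 4.8% at r = 2%, 4.4% at 5%, 3.9% at 10%. If not balanced, it stays near 5%: simulation gave 4.7% to 5.4% (Monte Carlo SE 0.2 points). Mean bias in the simulations was at most 0.005 SD. Unequal sites (90/60/30/20) gave interval-width ratios within 0.0005 of those for equal sites.

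**The case for a change.** The best case for acting is asymmetry. The most that a site term can cost here is about 0.6 power points, while plausible site differences would return several times that. The two-way label does not help the secondary models, and a reader cannot tell from section 4 what was fitted. A single sentence would settle it, and a rerun needs no new data.

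Two parts of this stand: the text leaves the second factor unnamed, and the term is cheap. What does not stand is the step from cheap to beneficial. Below a site share of about 1.5%, with allocation not balanced by site, adding site widens the interval. The gain is negligible at 2% or less, and nothing in the documents says which share applies or whether randomisation was stratified. Larger shares would give larger gains, but the documents offer no support for assuming them.

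Nor would the gain reach the main result. The title page gives completion in June 2020 and a report date of December 2020. Replacing the fitted primary model afterwards would be a post hoc choice, so a site-adjusted estimate could serve only as a sensitivity analysis, leaving the primary interval and test unchanged.

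**Conclusion.** No change to the plan follows. The documents leave out a detail, namely the second factor in the primary model and whether allocation was stratified by site. They do not show that site was left out. If site was fitted, the concern is already met. If it was not, the comparison is unbiased and the type I error is at or below nominal; the possible loss is one of efficiency.

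That loss runs from a gain of about 0.6 power points (leaving site out is slightly better) when sites do not differ and allocation is unbalanced, to about 1.4 points lost at a 5% site share and 2.8 to 3.4 at 10%. These figures rest on 200 analysed subjects, an assumed effect of 0.396 SD, a two-sided 5% test and assumed site shares. Whether to include a four-level factor of unknown value, with no stated stratification, is a reasonable judgement either way, and the results under the analysis as described remain sound.

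### Does listing a Wilcoxon test and a t-test beside the ANCOVA let the sponsor choose the test after seeing the data?

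*Combined protocol and SAP*

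**What the plan says.** All the relevant text is in Section 4 (Statistical Analysis Plan). On the primary variables: "The primary efficacy analyses, including FCS and ODS dryness, were performed using the last observation carried forward (LOCF) imputation method", in the ITT population at week 2. The treatment effect is "calculated by change from baseline in pre-controlled adverse environment (CAE) mode". The comparison with placebo was "tested versus placebo using a two-way ANCOVA model adjusting for baseline at $\alpha = 0.05". The next sentence reads: "A Wilcoxon rank sum test and a two-sample *t*-test were also assessed where appropriate".

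The continuous and ordinal secondary variables "were analyzed with an ANCOVA model adjusting for baseline and also evaluated with a two-sample" t-test, without imputation.

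Three things are absent: a criterion for when the Wilcoxon test or t-test applies, a label such as primary or supportive for any test, and a rule for results that disagree. The section is three short paragraphs in the past tense, and the title page dates study completion to June 2020 and the report to December 2020. It reads as a summary of what was done. A fuller plan may exist but is not in these documents.

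**The concern.** One primary hypothesis has up to three tests and each secondary variable has two. If any of them can carry a claim, the choice of test can follow the data and the error rate for that comparison exceeds its nominal level.

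The tests can also disagree. A t-test or rank-sum test on change does not adjust for baseline, so it is less precise than the ANCOVA, and a chance baseline imbalance can make one significant and the other not. Someone holding three p-values, an undefined condition and no rule for conflict could defend whichever is smallest. At stake is whether a positive finding on FCS or ODS dryness carries a 5% false-positive risk or a larger one.

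**Working it through.** **Inputs from the documents.** Alpha is 0.05, stated with the ANCOVA (Section 4). The analysed quantity is change from baseline, pre-CAE (Section 4). The title page gives the size: "phase 2/3 CAE study in approximately 200 subjects. (100 per treatment arm". Subjects were "randomized in a 1:1 ratio to receive placebo or BRM421 Ophthalmic Solution" (Section 3). There is no derived figure to reproduce: alpha is a nominal input, and the sample size comes without power, effect size or SD.

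**Assumptions, not in the documents.** Two-sided testing; baseline-to-week-2 correlation ρ from 0.2 to 0.9; normal, ordinal 0–5 or skewed outcomes; Wilcoxon and t-test applied to change scores; ANCOVA with treatment and baseline only, because the second factor of the two-way model is not named.

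**Step 1: the ANCOVA decides.** Null simulation, 100 per arm, 20,000 trials per scenario. The ANCOVA rejects in 4.7% to 5.1% of trials over all 15 scenarios. The Monte Carlo standard error is √(0.05 × 0.95 / 20,000) = 0.15 percentage points, so this agrees with 5%. The extra tests add nothing to this error.

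**Step 2: any of the three may win.** The same data sets, with all three tests always run, give the percentage with at least one p < 0.05:

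| Outcome | ρ = 0.2 | 0.3 | 0.5 | 0.7 | 0.9 |
|---|---|---|---|---|---|
| Normal | 8.7 | 8.5 | 8.2 | 7.4 | 6.8 |
| Ordinal 0–5 | 8.5 | 8.5 | 7.9 | 7.7 | 6.5 |
| Skewed | 9.6 | 9.5 | 9.2 | 8.8 | 8.3 |

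The range is 6.5% to 9.6%, or 6.5/5 = 1.3 to 9.6/5 = 1.9 times nominal. Three independent tests would give 1 − 0.95³ = 14.3%, but these tests share the same data, so that is only a ceiling. The secondary variables have two of the three tests, so the same choice there cannot exceed the table.

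**Step 3: precision.** With equal baseline and week-2 variance σ², change has variance 2σ²(1 − ρ) and the ANCOVA residual has σ²(1 − ρ²). The ratio is 2/(1 + ρ): 2/1.3 = 1.54, 2/1.5 = 1.33 and 2/1.7 = 1.18 at ρ = 0.3, 0.5 and 0.7. The t-test is the weaker test. That is harmless if it is supportive.

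**Step 4: two primary variables.** Taking the two as independent and letting either win, normal outcomes give 1 − (1 − 0.0853)² = 16.3% at ρ = 0.3 and 1 − (1 − 0.0743)² = 14.3% at ρ = 0.7. With one test per variable the same rule already gives 1 − 0.95² = 9.75%. Test choice accounts for about 4.6 to 6.6 points. The rest is endpoint multiplicity, a separate question, and the documents state neither independence nor an either-may-win rule.

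**Step 5: which rule does the text support?** Alpha is named once, with the ANCOVA. The primary comparison is said to be tested by that model, and the Wilcoxon test and t-test follow as things done in addition. The secondary variables repeat the pattern. No sentence lets an additional test replace the ANCOVA. Step 1 therefore describes the plan as written; Step 2 describes a rule that would have to be added to it.

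**The case for a change.** The strongest reply is that an implied hierarchy does not bind. Making the extra tests conditional on suitability suggests that for some data another test fits better than the ANCOVA, and the text does not say what follows. One sentence would close the gap at almost no cost. The change looks worthwhile either way: if any test can decide, error exceeds 5%; if only the ANCOVA can, the unadjusted tests supply weaker and sometimes conflicting p-values. Under the null with normal outcomes, another test is significant when the ANCOVA is not in 8.53 − 5.03 = 3.5%, 8.20 − 5.06 = 3.1% and 7.43 − 4.84 = 2.6% of trials at ρ = 0.3, 0.5 and 0.7.

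The drafting gap stands: the condition is undefined, and a rule for discordance would have been tidier. The rest does not lead to a change. The inflation needs a decision rule that the documents do not contain, and nothing in them shows that a test was picked after the data. Deleting the t-tests leaves the ANCOVA result as it is. Replacing the Wilcoxon test by a rank ANCOVA that cannot overturn the main analysis is a preference between supportive analyses; a rank-based check beside a parametric model is reasonable where some variables are ordinal. The trial is also complete, so a sentence written now would be post hoc unless it recorded a decision already taken.

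**Conclusion.** No change to the plan is needed. The missing label and the undefined condition are details that an analyst fills sensibly from the text: the ANCOVA, the only method given a significance level, decides, and the Wilcoxon test and t-test are robustness checks. On that reading the error per comparison is about 5%.

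The 6.5% to 9.6% range would matter only if a report claimed success on an additional test after a non-significant ANCOVA. It rests on two-sided testing and on assumed correlations and outcome shapes, with all three tests run every time. A reader of the results should take the ANCOVA p-value as the finding and treat disagreement from the other tests as information about robustness. Whether two primary variables need a multiplicity rule is a separate question that this conclusion does not settle.
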